Appendix

- I Performance Status
- II Staging System
- III EORTC QLQ-C30 version 3
- IV EORTC QLQ-H&N
- V Tobacco and Alcohol Assessment/Pre-treatment
- VI Sialometric Form

Version 2.0

Date: 6.21.2011

- VII Physician Dysphagia Log
 - VIII Patient Swallowing Diary
 - IX Videofluoroscopic Swallowing (VFSS) Evaluation
 - X Common Terminology Criteria for Adverse Events, Version 3.0 (CTCAE)
 - XI Speech Assessment/Head and Neck Health Status Assessment Inventory (HNHSAI)
 - XII ChemoSensory Questionnaire (CSQ)
 - XIII Trismus Assessment
 - XIV Audiology Form
-

SCHEMA

**A Phase II Study of Proton Radiotherapy with Chemotherapy for
Nasopharyngeal Carcinoma**

[figure not shown]
Combined Proton-Photon Radiotherapy

Primary site	70 CGE
Nodal Disease > 2cm	70 CGE
Nodal Disease 1 - 2cm	66 CGE
Primary subclinical	60 CGE
High risk nodal region	60 CGE
Low risk nodal region	50 CGE

Chemotherapy

Cisplatin 100mg/msq d1 (cycle 1), 22 (cycle 2), 43 (cycle 3)
5-FU 1000mg/msq 96hr
Cisplatin 80mg/msq

I. Concurrent Radiotherapy and Chemotherapy (Chemoradiation)

RADIOTHERAPY* Days 1  54
CISPLATIN** X

*Administered Monday through Friday, start date may be on a Monday, Tuesday, Wednesday, or Thursday

* *Cisplatin infusion to be given every 21 days during RT. First dose to be administered within the first three days of the start of radiation.

II. Adjuvant Chemotherapy – to begin 3 - 8 weeks after completion of chemoradiation

Day	1	2	3	4	29	30	31	32	57	58	59	60
Cisplatin	x				x				x			
5-FU	x	x	x	x	x	x	x	x	x	x	x	x

1.0 Background and Significance

1.1 Background

In the USA and Western Europe, nasopharyngeal carcinoma (NPC) accounts for less than 1% of malignancies. The average incidence increases 80-fold in endemic areas such as Southern China. NPC is a neoplasm that differs from other squamous cell carcinomas of the head and neck with regard to epidemiology, histologic features, treatment strategies, and treatment response. Due to the anatomical location, nasopharyngeal cancers are considered unresectable. The conventional treatment approach has been radiation. Local control rates with conventional once daily radiation are 75% or higher for Stage I and II diseases but decrease to 20 - 70 % for Stage III and IV diseases. For patients with advanced NPC (stage III - IV) treated with radiation alone, the 5-year survival rates are only 10 - 40% (1 - 7).

The predominant patterns of failure for locally advanced NPC are local recurrence and distant metastasis. In a retrospective analysis of 1301 patients with NPC, locoregional recurrence was shown to be an independent prognostic indicator of subsequent distant metastases (8). Achieving local control is therefore important in the treatment of nasopharyngeal carcinoma.

1.2 Combined radiation and chemotherapy is superior to radiotherapy alone

The standard of care of treatment in the United States is concurrent chemoradiation followed by adjuvant chemotherapy, based on the results of the Intergroup study (SWOG/RTOG/ECOG), which showed improved progression-free and overall survival with chemoradiation compared with radiation alone (9). The study compared radiotherapy (70 Gy) alone to chemotherapy concurrent with radiotherapy followed by adjuvant chemotherapy in patients with nasopharyngeal cancer. This revealed a statistically significant increase in 3-year progression-free survival (69% versus 24%) and 3-year overall survival (76% versus 46%) in favor of the chemoradiotherapy arm. Lin et Al recently reported increased progression-free and overall survival rates in patients who received 2 cycles of continuous cisplatin and fluorouracil chemotherapy during radiotherapy compared to radiotherapy alone in patients with locally advanced nasopharyngeal carcinoma in endemic areas (10). Chan et al in a randomized trial of 350 patients, showed that patients who received weekly cisplatin of 40 mg/m² during radiation had a prolonged progression-free survival compared to patients who received radiation alone (11). These studies suggest that concurrent chemoradiation with or without adjuvant chemotherapy is superior to radiotherapy alone in patients with locally advanced NPC in endemic and non-endemic areas.

1.3 Rationale of using proton radiotherapy

In the Intergroup randomized study, only 63% of patients received all three courses of concurrent cisplatin and 55% received all three courses of adjuvant chemotherapy.

Twenty-eight percent of patients in the radiotherapy alone arm experienced grade 3 and 4 mucositis compared to 37% in the chemoradiation arm. Two percent of patients in the radiotherapy arm experienced severe (grade 4) mucositis compared to 12% in the chemoradiation arm (9). In the randomized trial of concurrent weekly cisplatin with radiotherapy versus radiotherapy alone by Chan et al, the progression-free survival was not statistically significant between the two arms (11). The percentage of patients completing at least four cycles of chemotherapy during external radiotherapy was 78%. This number dropped to 60% and 44% for five and six cycles, respectively. In this study, mucositis was the most common reason of discontinuing chemotherapy. These data suggest that if one can reduce acute treatment toxicity from concurrent chemoradiation, one may increase treatment compliance and therefore treatment outcome.

Because of the anatomic location of the nasopharynx, radiation treatment with and without chemotherapy is associated with significant treatment-related toxicity such as brain necrosis, audio-visual toxicity, radiation encephalopathy, radiation myelitis, and cranial nerve paralysis. Xerostomia and swallowing dysfunction are also the major complaints in patients who have undergone conventional external beam radiation therapy to the nasopharynx. Protons are charged particles, with similar biological effect as X-rays. The advantage of protons lies in their physical dose distribution. Due to the defined range of protons (i.e. Bragg peak), dose distribution can be designed that conforms more closely to the tumor volume (12). This superior physical property of proton allowed less radiation to the normal surrounding tissues, therefore expected to result in decreased acute and late toxicities.

The goal of using proton therapy is therefore to: 1) test the hypothesis that reduction of radiation dose to normal tissue can reduce acute toxicity and increase treatment compliance to the combined modality treatment and 2) to decrease late toxicity and improve health related quality-of-life outcomes.

1.4 Preliminary experience of proton radiotherapy for T4 nasopharyngeal carcinoma

At the Massachusetts General Hospital, proton beam radiotherapy has been used to treat locally advanced nasopharyngeal carcinoma. Between 1990 and 2002, 17 patients with newly diagnosed T4 N0-3 nasopharyngeal carcinoma received combined conformal proton and photon radiotherapy. Seventy-one percentage of patients had World Health Organization type 2 - 3 histology. The median prescribed dose to the gross target volume was 73.6 Cobalt-Gray-Equivalent (CGE) (range 69 - 76.8). Eleven patients received accelerated hyperfractionated radiotherapy. Ten patients received induction or concurrent chemotherapy. All patients except one completed the planned concurrent radiation and chemotherapy treatments. With a median follow-up of 43 months, 1 and 2 patients developed local and systemic failures, respectively. There was no neck recurrence. The locoregional control and relapse-free survival rates at 3 years were 92% and 79%, respectively. For patients who received chemotherapy, the 3-year

relapse-free survival rate was 91% compared to 50% for those without chemotherapy (p = 0.09). The 3-year overall survival rate was 74%. For patients who received chemotherapy, the 3-year overall survival rate was 91% compared to 40% for those without chemotherapy (p = 0.01). This preliminary experience suggests that combined use of chemotherapy with proton radiotherapy results in improved disease-free and overall survivals in patients with T4 nasopharyngeal carcinoma (13).

2.0 Objectives

2.1 Primary Objectives

- (1) To test the hypothesis that reduction of radiation dose to normal tissue can reduce acute toxicity and increase treatment compliance to combined modality treatment.
- (2) To assess health related quality-of-life outcomes after proton radiotherapy for nasopharyngeal carcinoma using objective measurements and validated quality-of-life instruments.

2.2 Secondary Objectives

To determine the rate and pattern of locoregional tumor recurrence in patients treated with proton beam radiotherapy and concurrent chemotherapy followed by adjuvant chemotherapy in patients with Stage II - IVA nasopharyngeal cancer.

3.0 Subject Selection

3.1 Patient Eligibility

- 3.1.1 Biopsy proven stage \geq T2b and/or node positive (American Joint Committee on Cancer Sixth Edition, Stage IIB – IVB) non-metastatic, squamous cell carcinoma of the nasopharynx, types WHO I - III.
- 3.1.2 No head and neck surgery of the primary tumor or lymph nodes except for incisional or excisional biopsies.
- 3.1.3 Zubrod performance status 0 - 1 or Karnofsky 70 or above.
- 3.1.4 All patients must undergo pre-treatment evaluation of tumor extent and tumor measurement.
- 3.1.5 Nutritional and general physical condition must be considered compatible with the proposed chemoradiation treatment.
- 3.1.6 Signed study-specific informed consent prior to study entry.
- 3.1.7 Patients must have a WBC \geq 4,000/ μ l and a platelet count of \geq 100,000/ μ l; patients must have adequate renal function as documented by creatinine clearance \geq 60 ml/min (actual or calculated by the Cockcroft-Gault method).
- 3.1.8 Age 18 or above
- 3.1.9 No active alcohol addiction (as assessed by medical caregiver).

3.1.10 Women of childbearing potential must have a negative pregnancy test.

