4.0 Pre-study Investigations

Each patient must have completed the following studies prior to study entry unless otherwise indicated.

- 4.1 Complete history and physical exam including weight, height, performance status, neurological examination, and vital signs within 14 days of study.
- 4.2 Complete descriptive documentation of the extent of the primary and regional disease (*if any*).
- 4.3 Completion of the following laboratory studies within 14 days of study entry: Complete Blood Count (WBC, neutrophils, platelet counts); serum creatinine, creatinine clearance, BUN; Chemistry (electrolytes, magnesium, and calcium); serum pregnancy test for women of childbearing. Completion of the following laboratory studies within 14 days of study entry: liver function tests including AST, bilirubin, alkaline phosphatase.
- 4.4 Completion of the following radiologic studies within 1 month prior to study entry: chest X-ray or CT; CT of head and neck with ≤ 2.5 mm contiguous slices in immobilization system (*with contrast, unless contraindicated*); or MRI of nasopharynx/base of skull with T1 contrast with gadolinium and T2 sequences required unless contraindicated; liver CT or MRI (*must be done only in the*

Version 2.0

Date: 6.21.2011

-

presence of elevated alkaline phosphatase, AST or bilirubin or other clinical indicator); bone scan (only in the presence of elevated alkaline phosphatase or other clinical indicator). The use of PET/CT scan is optional but encouraged. Treatment planning CT can be used but must be within 21 days of start of radiation.

4.5 Thyroid function panel.

4.6 Audiogram.

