5.9 Speech Assessment/Head and Neck Health Status Assessment Inventory (HNHSAI)

5.10 ChemoSensory Questionnaire (CSQ)

5.11 Trismus Assessment

Subject Enrollment

Patients will be registered through the Quality Control Committee (QCC) at the Dana-Farber Cancer Institute [contact], [contact]) prior to treatment. Any patient not registered to the protocol prior to the initiation of treatment will be ineligible. The following information will be provided to the QCC:

Name and telephone number of primary oncologist

Protocol name

Patient name, date of birth, and ID number

Primary institution

Date of initiation of radiotherapy

Confirmation of eligibility

Copies of consent form with signatures

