6.5.6 Cisplatin Dose Adjustments

6.5.6.1 Neutropenia

Treatment can be delayed for up to 2 weeks until ANC is $\geq 1500/\text{mm}^3$. However, if the counts have not recovered in 2 weeks, the patient should go off chemotherapy. Dose reductions for reduced ANC are not based on a single nadir count. The ANC must remain $< 500/\text{mm}^3$ for > 5 days before a dose reduction is made. If the results of the scheduled weekly complete blood count documents an ANC of $< 500/\text{mm}^3$, repeat counts are to be obtained every other day until the ANC recovers to a level of $> 500/\text{mm}^3$. If chemotherapy must be withheld due to neutropenia, complete blood count should be obtained weekly until the counts reach the lower limits for treatment as outlined.

Table 6. Cisplatin dose modifications in neutopenia

Nadir of last cycle		% Dose of cisplatin from starting dose
	ANC* on day 1 of each cycle < 1500	ANC* on day 1 of each cycle ≥ 1500
Febrile neutropenia (regardless of duration)	Hold	100%
< 500 for < 5 days	Hold	100%
< 500 for ≥ 5 days	Hold	80%

* ANC = absolute neutrophil count

ANC must be $\geq 1,500/\text{mm}^3$ on day 1 of each cycle. Reduce doses only for ANC is $< 500/\text{mm}^3$ for ≥ 5 days.

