6.5.6.2 Thrombocytopenia

Chemotherapy must not be administered until platelets are $\geq 100,000$. If chemotherapy must be withheld due to thrombocytopenia, platelet counts should be obtained weekly until the counts reach the lower limits for treatment as outlined. Treatment is based upon the nadir count of the last cycle of chemotherapy as follows:

Table 7. Cisplatin dose modifications in thrombocytopenia

Nadir of last cycle		% Dose of cisplatin from starting dose
	Platelets on day 1 of each cycle < 100,000	Platelets on day 1 of each cycle ≥ 100,000
$\geq 50,000$	Hold	100%
< 50,000 (1 st occurrence)	Hold	80%
< 50,000 (2 nd occurrence)	Hold	60%

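### Criterion 3.1.7 sets no neutrophil limit, so a patient can be registered with a screening ANC that, if it persists to day 1, would not allow cycle 1 under section 6.5.6.1

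*Combined protocol and SAP*

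**What the plan says.** - **Entry (3.1.7).** "Patients must have a WBC" of at least 4,000/µl, platelets of at least 100,000/µl and creatinine clearance of at least 60 ml/min. No criterion in 3.1 or 3.2 names a neutrophil count.
- **Screening (4.3).** The tests within 14 days of study entry include "Complete Blood Count (WBC, neutrophils, platelet counts"), so the neutrophil count is known before entry. No threshold is attached to it.
- **Registration (Subject Enrollment, after 5.11).** "Any patient not registered to the protocol prior to the initiation of treatment will be ineligible". The items to be supplied include "Confirmation of eligibility".
- **Dosing (6.5.6.1).** The note under Table 6 requires an ANC of at least 1,500/mm3 "on day 1 of each cycle. Reduce doses only for ANC is" below 500/mm3 for 5 days or more. Treatment may wait up to two weeks; "if the counts have not recovered in 2 weeks, the patient should go off chemotherapy". The rows of Table 6 are indexed by "Nadir of last cycle".
- **Platelets, for comparison (6.5.6.2).** "Chemotherapy must not be administered until platelets are" at least 100,000, the same figure as at entry.
- **Endpoint (11.0 and 12.0).** Compliance is defined partly by the number of chemotherapy courses received. The test succeeds if at least 18 of 25 patients complete all six cycles.

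**The concern.** The entry rule and the dosing rule use different white-cell measures. Entry looks at total WBC; cisplatin dosing looks at neutrophils. A patient can pass the first and fail the second, and the count that would show this is already in hand at screening. Registration must precede treatment, so the patient is enrolled before the day-1 rule is applied.

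This matters because the main test counts completed chemotherapy cycles as evidence that protons make chemoradiation more tolerable. A patient who never receives chemotherapy because of a baseline blood count says nothing about proton tolerance, yet could be counted as a failure. Section 12 gives no replacement rule for such a patient.

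**Working it through.** **1. The plan's own figures.** Inputs from section 12: n = 25, success at 18 or more, null rate 55%, target rate 77%. With X binomial:

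- P(X ≥ 18 | n = 25, p = 0.55) = 0.0639, stated as 6%.
- P(X ≥ 18 | n = 25, p = 0.77) = 0.8011, stated as 80%.

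Both reproduce to the stated rounding. The rule leaves room for 25 − 18 = 7 non-completers.

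**2. Entry and dosing limits side by side.**

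| Item | Entry | Cisplatin dosing | Comparison |
|---|---|---|---|
| Platelets | ≥ 100,000 (3.1.7) | ≥ 100,000 (6.5.6.2) | Same |
| Creatinine clearance | ≥ 60 ml/min (3.1.7) | ≥ 60 ml/min for full dose (Table 8) | Same figure, but Table 8 is triggered by a rise in creatinine, not by a check before every cycle |
| Neutrophils | None | ≥ 1,500/mm3 on day 1 (6.5.6.1) | No entry limit |
| Hearing | Excluded above grade 2 (3.2.10) | Half dose at grade 1 or 2 if continued (6.5.6.4) | Differs, but a dose can still be given |

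Platelets are the clean parallel. For neutrophils, a value below the limit permits no dose.

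**3. Which eligible patients fall below the limit.** ANC = WBC × neutrophil fraction (1 µl = 1 mm3). The fraction below which ANC is under 1,500 is 1,500 / WBC:

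- WBC 4,000: 1,500 / 4,000 = 37.5%
- WBC 5,000: 1,500 / 5,000 = 30%
- WBC 6,000: 1,500 / 6,000 = 25%

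Example: 4,000 × 0.35 = 1,400, which is below 1,500. This patient meets 3.1.7.

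**4. From a low screening count to a lost completion.** Each of these steps is needed:

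1. The low ANC is still present on day 1. The day-1 count governs dosing, and the screening count may be up to 14 days older than study entry.
2. Cycle 1 is then held. This is a delay of up to two weeks, not a missed cycle.
3. The count stays below 1,500 for the whole two weeks.
4. The two-week rule is applied to a patient who has had no dose. This is an inference: the sentence speaks of recovery, and Table 6 is indexed by the previous cycle's nadir.
5. The patient is counted in the 25 as a non-completer. Section 12 does not say so, but gives no rule for replacing such a patient.

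If all five hold for one patient, 1 of the 7 permitted non-completions is used. The documents give no frequency for any step.

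**The case against.** The strongest reply is that WBC at entry with an ANC check on day 1 is a workable arrangement. The screening count itself stops nothing: an ANC of 1,400 at screening may be 1,500 or more on day 1. If it is not, the protocol provides a hold, and neither section 11 nor section 12 treats a late cycle as a missed one. A full two-week hold could strain the concurrent schedule, since the schema wants the first cisplatin dose within three days of starting radiation, but the cycle is delayed rather than lost. All of this stands, and it limits the point to persistently low counts.

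It can also be said that 3.1.5 requires a physical condition compatible with chemoradiation and that 3.2.6 excludes major illness that would interfere with completion. These let an investigator decline such a patient, but they rest on judgement and give no count. Platelets and clearance were given explicit numbers despite them.

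A third reply is that 6.5.6.1 was written for patients already dosed. That weakens the stopping step, as noted in the working. But the note under Table 6 covers each cycle without exempting the first. If it were read as excluding cycle 1, the protocol would set no neutrophil limit at all for the first cisplatin dose, so the change would still be worthwhile.

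A reader might infer more than the documents support in two ways:

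- **That an eligible patient with a low screening ANC is necessarily barred from cycle 1 and lost to the endpoint.** The chain in the working is conditional at every step.
- **That the design loses power.** With one certain non-completer and 77% completion in the other 24, P(X ≥ 18 | n = 24, p = 0.77) = 0.694. That calculation assumes such a patient occurs and applies 77% only to the rest, whereas section 12 gives 77% as the rate for all patients. It is not evidence of a power loss.

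**Conclusion.** The mismatch is real on the text: no entry criterion limits neutrophils, while 6.5.6.1 sets a day-1 minimum for every cycle. A patient with WBC 4,000 and ANC 1,400 can be eligible and registered, and could not be given cycle 1 if that count persisted.

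The size is small. At most, each such patient would use one of 7 permitted non-completions for a reason unrelated to proton tolerance. That rests on two assumptions: that the two-week rule is applied before the first dose, and that an undosed patient stays in the denominator. Such patients are probably rare, though the documents give no frequency. The stated 6% significance level and 80% power are correct as computed and are not affected. Severity is minor.

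**What to change.** Add an ANC of at least 1,500/mm3 to criterion 3.1.7, judged on the count already drawn under 4.3, and keep the day-1 check in 6.5.6.1 to deal with any fall between screening and treatment. Entry and dosing would then use the same neutrophil limit, as they already do for platelets.

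The change is one line and needs no new test. It has two downsides. A rare patient with adequate WBC but low neutrophils would not be enrolled. Eligibility would also become slightly tighter while success is still judged against the Intergroup study's 55%. The documents do not give that study's entry criteria, so one cannot tell whether it applied a similar limit; if it did not, the tighter criterion could slightly favour the trial's completion rate for reasons other than protons.

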3.2 Exclusion Criteria

- 3.2.1 Stage IVC or evidence of distant metastases.
- 3.2.2 Previous irradiation for head and neck tumor.
- 3.2.3 Patient is on other experimental therapeutic cancer treatment.
- 3.2.4 Other malignancy except non-melanoma skin cancer or carcinomas not of head and neck origin and have been controlled for at least 5 years.
- 3.2.5 Active untreated infection.
- 3.2.6 Major medical or psychiatric illness, which in the investigators' opinions, would interfere with either the completion of therapy and follow-up or with full and complete understanding of the risks and potential complications of the therapy.
- 3.2.7 Prophylactic use of amifostine or pilocarpine is not allowed.
- 3.2.8 Pregnant or breast feeding women, or women and men of childbearing potential not willing to use adequate contraception while on treatment and for at least 3 months thereafter.
- 3.2.9 Symptomatic peripheral neuropathy \geq grade 2 by National Cancer Institute Common Toxicity Criteria (CTCAE)
- 3.2.10 Symptomatic altered hearing $>$ grade 2 by CTCAE.

4.0 Pre-study Investigations

Each patient must have completed the following studies prior to study entry unless otherwise indicated.

- 4.1 Complete history and physical exam including weight, height, performance status, neurological examination, and vital signs within 14 days of study.
- 4.2 Complete descriptive documentation of the extent of the primary and regional disease (*if any*).
- 4.3 Completion of the following laboratory studies within 14 days of study entry: Complete Blood Count (WBC, neutrophils, platelet counts); serum creatinine, creatinine clearance, BUN; Chemistry (electrolytes, magnesium, and calcium); serum pregnancy test for women of childbearing. Completion of the following laboratory studies within 14 days of study entry: liver function tests including AST, bilirubin, alkaline phosphatase.
- 4.4 Completion of the following radiologic studies within 1 month prior to study entry: chest X-ray or CT; CT of head and neck with ≤ 2.5 mm contiguous slices in immobilization system (*with contrast, unless contraindicated*); or MRI of nasopharynx/base of skull with T1 contrast with gadolinium and T2 sequences required unless contraindicated; liver CT or MRI (*must be done only in the*

Version 2.0

Date: 6.21.2011

-

presence of elevated alkaline phosphatase, AST or bilirubin or other clinical indicator); bone scan (only in the presence of elevated alkaline phosphatase or other clinical indicator). The use of PET/CT scan is optional but encouraged. Treatment planning CT can be used but must be within 21 days of start of radiation.

4.5 Thyroid function panel.

4.6 Audiogram.

